16.3.2. Case Report Forms (CRFs)

Case report forms will be created following protocol finalization and approval to capture study data. These forms may be in the form of paper, or may be electronic (e-CRFs). An eCRF system, provided by an independent third-party vendor, may be used to capture data. Prior to deployment of the study, the eCRF system will be validated and specified to address source documentation, in accordance with Sponsor and regulatory requirements.

16.3.3. Data Storage and Access

In case of eCRF, data will be entered into the CTMS system, checked for discrepancies and queried for any issues in accordance to site-approved SOPs. The database housing the eCRF input will be hosted by the eCRF vendor and paper CRFs will be used as the backup plan, if deemed necessary and applicable. Official corrections and/or modifications during the trial will be automatically tracked by an audit trail detailing the date, time, and personnel involved/approving the modification of the eCRF. All vendor data access and entry can only be performed by authorized users, using a unique user login and password. The Sponsor and dicentra will permit trial-related monitoring, audits, IRB review, and regulatory inspections, providing direct (read-only) access to source data/documents. Paper CRFs will be monitored for completion, queried through internal review by delegated site staff, identified items resolved and documented where applicable, and any required data from source documents will be entered into the final database prior to locking.

16.4. Data Quality Assurance

Data cleaning will be performed to check for completeness and consistency of data using both programmed and manual edit checks. Discrepancies in data will be resolved through querying, delegation and resolution in accordance to site SOPs. Actions changing original data collection will be recorded using an electronic audit trail or done manually for paper CRFs according to ICH-GCP E6(R2).

Appendix 1: Questionnaires TNSS Questionnaire

21-AAHSE-01 – SSH Corp.

Visit #:

Participant ID: -
ABC ###

Date of Visit: / /
MMM DD YYYY

Total Nasal Symptom Score

Please answer all questions to the best of your ability. This information will assist us in understanding and treating symptoms.

Please rate the following rhinitis symptom for the last week:

1. Nasal obstruction

No Symptoms	0
Mild – awareness but not troubled	1
Moderate – troublesome but not interfering with normal daily activities or sleep	2
Severe – interfering with normal daily activities or sleep	3

2. Itching/Sneezing

No Symptoms	0
Mild – awareness but not troubled	1
Moderate – troublesome but not interfering with normal daily activities or sleep	2
Severe – interfering with normal daily activities or sleep	3

3. Secretion/runny nose

No Symptoms	0
Mild – awareness but not troubled	1
Moderate – troublesome but not interfering with normal daily activities or sleep	2
Severe – interfering with normal daily activities or sleep	3

Total Score:
 9

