For the control group, the same investigational product will be administered, however the procedure for use will be modified as follows: There will be no mouth cleaning before the product consumption (No step 1 as mentioned above). The product will be swallowed instead of dissolved in the mouth, in order to reduce its presence in the mouth as much as possible. The purpose of this control group is to support the effect of use of the entire two-step method as compared to the investigational group.

The active ingredient, L-Arginine is known to Health Canada. L-Arginine is listed in the NHPID, and allowed for use in NHPs under proposed here conditions of use. Safety of the of current ingredient combination, while allowed for use separately, will also be tested under proposed conditions of use.

The Rationale for Performing Research:

Increase in immune-mediated conditions [30]–[32](Allergic rhinitis is one of them) and the few medical solutions available (each of which is associated with side effects) prompted this research and clinical study. The medicinal ingredient, L-Arginine, in the formulation of AllerPops is a well-known Natural Health Product Ingredient with history of human use.

4. Study Objectives

Objectives:

Primary Objective: To assess the effectiveness of AllerPops on relieving nasal symptoms compared to the control group in volunteers with seasonal and perennial (or intermittent and persistent) allergic rhinitis during the first 7 days of the 21-day intervention period.

Secondary Objectives:

1. To evaluate the safety of AllerPops administration in volunteers with seasonal/year-long allergies during a 21-day intervention period.
2. To assess the duration of effectiveness of AllerPops in relieving nasal symptoms compared to the control group in volunteers with seasonal/year-long allergies during a 21-day intervention period (exploratory).

3. To evaluate the effect of the AllerPops administration on the oral microbial presentation/microbiota using Amplicon Metagenomics Sequencing test through saliva samples during a 21-day intervention period (exploratory).
4. To evaluate the effect of the AllerPops administration on the IgE (total) blood level during a 21-day intervention period (exploratory).

Endpoints:

Primary Endpoint: The reduction of nasal allergic symptoms during the first 7 days of the 21-day intervention period (once every other day – D1, D3, D5). The reduction of symptoms will be measured using the following assessments.

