6.4 Directions

IMPORTANT: Must be fasting for at least 4 hours before taking the study product.

Directions for the Investigational Group:

1. Brush teeth with tap water (no toothpaste).
2. Scrub tongue with disposable tongue scraper provided. (**Caution:** *reaching too far may cause a gag reflex.*)
3. Gargle and swish hot (optimal 120°F) water for 10-20 seconds. Spit out and repeat gargling over the next 5 minutes. The tongue should be red and without any biofilm. If it is not, repeat *Step 2*, and gargle once more.
4. Self-administer one lozenge. Let the lozenge slowly melt in the mouth. Do not chew or swallow whole. This may take up to 60 minutes. Discard if it is not fully dissolved after 60 minutes. Wait at least 30 minutes before eating your next meal.
5. Repeat *Step 1* to *Step 5* every other day for a minimum of 3 doses.
6. After the 3rd dose, you may repeat *Step 1* to *Step 5* every other day until you are satisfied with the symptom relief up to and including Day 13. Do not take the product on Day 14 onwards and return all remaining product at Visit 4.

Directions for the Control Group:

1. A box containing 8 units of the Investigational Product will be dispensed. This box will only be dispensed once, at visit 2.
2. Microwave: heat the product in 5 second increments until soft. (Caution: more than 10 seconds of microwaving the product may cause it to burn).
3. Cut: cut the product into smaller pieces those are the size of your usual medication/supplement.
4. Swallow: Participant will be instructed to swallow each of the small pieces over time with plenty of warm water. The participant will also be allowed to have a few sips of water to moisten the mouth and throat prior to swallowing the control product, if they feel it is necessary. Wait at least 30 minutes before eating your next meal. For next 2 doses, you must repeat *Step 2* to *Step 4* once every other day (day 3 and day 5).
5. After the 3rd dose, you may choose to use additional doses until you are satisfied with the symptom relief. If you choose to continue using the product, you must repeat *Step 2* to *Step 6* once every other day up to (and including) day 13. Maximum dose expected during day 1 to 13 is 7. Do not take the product on day 14 onwards and return all remaining product at visit 4.

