 - Serum creatinine
 - Potassium
 - Chloride
 - Sodium
 - IgE (total)
8. Be provided with a paper/electronic diary – IP dosing, adverse events, concomitant medication.
9. Be provided with the IP (and oral hygiene kit if applicable) and instructions on dosing.
10. Be provided with dates/times of subsequent visit(s).
11. Review of all information for the visit by the PI and/or delegate prior to the next study visit to determine continued safe participation.

The participant will be given a paper/electronic daily diary in order to record the use of concomitant medications, IP dosing, symptoms, and any adverse events (such as fatigue, fever or headache) that may have occurred. The diary will be collected and/or reviewed at the research site at each visit as indicated on the Schedule of Assessments.

The participant should take the IP after this visit at home. The participant should take AllerPops at a maximum frequency of once every other day until the next study visit (Day 7). The participant should not take the product the morning of the next visit. The designated maximum dose until the next visit on day 7, is 3 doses.

Visit 3 – Follow-Up – Day 7 ± 1

These assessments may not be completed in the order shown below.

Participants:

1. Must be at least 8 hours fasting (no food, only water) prior to visit.
2. Will have any changes to health reviewed by delegated study staff.
3. Study diary will be collected and/or reviewed by delegated study staff for completion, and any AEs and/or concomitant medications.
4. For females of childbearing potential, a urine sample will be collected for a urine pregnancy test.

5. Will have the following measurements taken: temperature, blood pressure, heart rate.
6. Will have the following saliva test:
 - Amplicon Metagenomics Sequencing
7. Will complete the following assessments:
 - Total nasal symptoms score (TNSS) questionnaire
 - Peak nasal inspiratory flow (PNIF) measurement
8. Will have the following blood tests:
 - CBC (WBC, RBC, Hb, HCT, MCV, MCH, MCHC, Platelet Count)
 - Aspartate aminotransferase (AST)
 - Alanine aminotransferase (ALT)
 - Bilirubin
 - Gamma-glutamyl transferase (GGT)
 - Alkaline phosphatase (ALP)
 - Serum creatinine
 - Potassium
 - Chloride
 - Sodium
 - IgE (total)
9. Be reminded to complete daily diary.
10. Review of all information for the visit by the PI and/or delegate prior to the next study visit to determine continued safe participation.

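### The Visit 3 TNSS recalls a full week, but Visit 3 can fall as early as Day 6 after a first dose on Day 1, so untreated days enter a primary score

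*Combined protocol and SAP*

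**What the plan says.** Section 4 defines the primary endpoint as "The reduction of nasal allergic symptoms during the first 7 days of the 21-day intervention period", with doses "once every other day – D1, D3, D5". Section 11.3.1 makes the change in TNSS between Visit 2 (Day 1) and Visit 3 (Day 7), compared between arms, a primary variable. PNIF over the same interval is the other.

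The TNSS form in Appendix 1 carries one instruction for every visit: "Please rate the following rhinitis symptom for the last week". Section 9.5 gives no other recall period.

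Section 8 fixes the timing. On dosing after Visit 2: "The participant should take the IP after this visit at home". The next visit is headed "Visit 3 – Follow-Up – Day 7 ± 1", so Days 6, 7 and 8 are all allowed. The daily diary issued at Visit 2 records symptoms, but Section 11 names no analysis that uses it.

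On doses before Visit 3, Section 8 (Visit 2) says: "The designated maximum dose until the next visit on day 7, is 3 doses". Section 6.4 lets the investigational group continue after the third dose "every other day until you are satisfied with the symptom relief up to and including Day 13", and the Visit 3 text in Section 8 lists Day 7 among the optional later dosing days.

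**The concern.** A seven-day recall at Visit 3 fits the treated period only if at least seven days have been treated. Day 1 and Day 6 are five days apart, and Day 1 and Day 7 are six. The recall can therefore reach back before the first dose, into days that the participant already rated at Visit 2. Those days then count in both the before and the after score.

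Untreated days look the same in both arms. Including them pulls the Visit 3 score towards baseline, shrinks the between-arm difference in change, and makes that difference depend on the day for which the visit was booked. At stake is the sensitivity of one of the two primary variables.

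**Working it through.** **Inputs.** Recall of 7 days (Appendix 1). First dose on Day 1 after Visit 2, and Visit 3 on Day 6, 7 or 8 (Section 8). Standardised effect 0.6, 80% power, t test for two independent means, 72 participants and p < 0.05 (Section 11.1). Equal allocation (Section 6.6), so 36 per arm.

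**Step 1: the plan's sample size.** Power comes from the noncentral t distribution with 2n − 2 = 70 degrees of freedom and noncentrality d × √(n/2) = 0.6 × √18 = 2.55.
- One-sided 0.05: 36 per arm are needed, 72 in total, with power 80.9%. This reproduces the stated number.
- Two-sided 0.05: 45 per arm are needed, 90 in total. With 72, power is 70.9%.

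The text does not state sidedness and the G*Power figure is not available here, so both are carried forward.

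**Step 2: untreated days in the recall.** The form does not say whether the visit day counts. Reading A takes the seven days before the visit; reading B counts the visit day as one of the seven. Day 1 is treated as a dosed day.

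| Visit 3 | A: days recalled | A: untreated | B: days recalled | B: untreated |
|---|---|---|---|---|
| Day 6 | −1 to 5 | 2 | 0 to 6 | 1 |
| Day 7 | 0 to 6 | 1 | 1 to 7 | 0 |
| Day 8 | 1 to 7 | 0 | 2 to 8 | 0 |

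This count is slightly lenient, because Day 1 before the dose is also untreated. By elapsed time, with both visits at the same clock hour and the dose 0 to 12 hours later, untreated time is 2.0 to 2.5 days at Day 6, 1.0 to 1.5 at Day 7 and 0 to 0.5 at Day 8.

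**Step 3: dilution.** Assume that participants average over the recalled days, that the effect is full from Day 1, that 0.6 is the undiluted effect, and that the SD is unchanged. Then diluted d = 0.6 × (treated days / 7).

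Visits spread evenly over Days 6 to 8:
- Reading A: (5 + 6 + 7)/21 = 6/7, so d = 0.514.
- Reading B: (6 + 7 + 7)/21 = 20/21, so d = 0.571.

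Every visit on Day 6, as a bound:
- Reading A: 5/7, so d = 0.429.
- Reading B: 6/7, so d = 0.514.

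**Step 4: power with 36 per arm.**

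| Case | d | Two-sided | One-sided |
|---|---|---|---|
| No dilution | 0.600 | 71% | 81% |
| Even spread, B | 0.571 | 67% | 78% |
| Even spread, A | 0.514 | 58% | 70% |
| All Day 6, B | 0.514 | 58% | 70% |
| All Day 6, A | 0.429 | 43% | 56% |

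**Step 5: the Day 8 visit.** The Visit 2 text in Section 8 caps doses before Visit 3 at three. Section 6.4 and the Visit 3 text in Section 8 permit a Day 7 dose. For a participant seen on Day 8 these cannot all be followed as written.

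**The case against.** The best defence is that the form matches the endpoint at the nominal visit. With Visit 3 on Day 7 and the visit day counted, the recall is exactly Days 1 to 7, the period named in Section 4. That stands for this one reading. It does not cover Day 6 on either reading, or Day 7 if the recall means the seven days before the visit.

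The power figures are also open to challenge. Section 11.1 does not link 0.6 to any particular scale. If it already describes the TNSS as administered, shrinking it counts the dilution twice. Averaging over recalled days is assumed, and so is the spread of visits. This stands: the day counts come from the documents, the power figures are illustrations. The all-Day-6 case in particular is a bound, since nothing suggests that every visit would be booked at the edge of the window.

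A reader might go further in three ways, none of which the documents support.
- *The score is defective because much of the recall precedes the third dose.* The endpoint is relief over the first seven days, so covering those days is by design. Three doses is a dosing minimum, and nothing says that benefit begins only after it.
- *The comparison is biased towards one arm.* Both arms have the same form, window and dosing days.
- *Visits 4 and 5 need a shorter recall too.* Their TNSS data are exploratory (Sections 4 and 11.3.3). A three-day recall at Visit 4 would in any case still take in a permitted dosing day in nine of the ten combinations of visit day and reading.

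**Conclusion.** The concern holds for untreated days in the Visit 3 TNSS: one or two whole days at a Day 6 visit, none or one at Day 7 plus the undosed part of Day 1, and no whole day at Day 8. The consequence is lost sensitivity and dependence on booking day in one of two primary variables. PNIF is measured at the visit and is untouched, so the primary assessment as a whole is not undermined.

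Under the stated assumptions and an even spread of visits, the loss is 4 to 13 percentage points of power two-sided (71% to 67 or 58%) and 3 to 11 one-sided (81% to 78 or 70%). Confidence is high in the day counts and lower in the size of the effect. This is a worthwhile, inexpensive improvement and not a fatal flaw.

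**What to change.** 1. Change the Visit 3 window to Day 7 or 8 (0/+1). This alone is not enough: under reading A a Day 7 visit still recalls Day 0.
2. On the Visit 3 form, replace the one-week recall with symptoms since the first dose of study product. For randomised participants who never dosed, ask about symptoms since Visit 2, so that everyone in the intention-to-treat analysis can answer. This step removes the untreated days; step 1 then keeps coverage of the seven-day period close to complete and similar across participants.
3. Print the three TNSS items, scored 0 to 3, in the existing daily diary. Report mean daily TNSS by arm for Days 1 to 7 as a supportive analysis.
4. Reconcile Section 6.4 with the Visit 2 and Visit 3 texts of Section 8 on a Day 7 dose when Visit 3 falls on Day 8. Which rule applies is for the sponsor and the investigator to settle.

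The cost is one fewer permitted visit day, new wording on one form, and three tick-boxes a day. The Visit 2 and Visit 3 recall periods will differ slightly in length, equally in both arms. The Visit 4 and 5 forms can stay as they are.
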